12.7 Annual Development Safety Update Reports (DSUR)

In addition to the expedited reporting above, CRUK will submit a DSUR in accordance with ICH E2F to the Competent Authority (MHRA in the UK) and the REC.

13 DATA ANALYSIS AND STATISTICAL CONSIDERATIONS

13.1 Description of statistical methods

All statistical aspects of the study will be fully documented in a comprehensive Statistical Analysis Plan authored by the study statistician and agreed by the independent Trial Steering Committee.

The primary outcome will be an exploration of camostat safety and toxicity, in terms of the number and severity of AEs and SAEs.

Descriptive statistics will be used to describe the demographics for each randomised group and overall. For categorical data, frequencies will be reported, and for continuous variables means and standard deviations, or for skewed data, medians and interquartile ranges will be reported.

Secondary outcomes will be reported in a similar way to the demographic data, with an estimate of the difference and standard error between the treatment groups for continuous or ordinal scale data. Medians and IQRs will be used where data are non-normally distributed. Absolute percentage difference and standard error will be reported for binary variables. Kaplan-Meier plots and life tables will be used to estimate median survival times

Subgroups will be explored where there are sufficient patients in each group. Data will be split by age (< 65 years vs ≥ 65 years), fall in lymphocyte ($<20\%$ fall vs $\geq 20\%$ fall), and neutrophil:lymphocyte ratio (<2.18 vs ≥ 2.18) for key explanatory variables.

No significance testing will be performed. Differences between treatment groups will be reported solely to inform future trials.

All enrolled patients who receive at least one dose of camostat in the treatment arm and complete Day 1 in the control arm will be evaluable for safety.

In order to be evaluable for efficacy, treatment arm patients must receive camostat for a minimum of five days, and control arm patients must either complete up to Day 14 or come off trial at an earlier timepoint due to an endpoint (e.g. hospitalisation).

Safety data will be collected from the date of written, or verbal, consent. Safety variables will be summarised by descriptive statistics.

Adverse events will be reported as tables of frequency of AEs by MedDRA system organ class and by worst severity grade observed. Tables should indicate related and unrelated events

Adverse events will be reported for each arm and presented as tables of frequency of AEs by MedDRA system organ class and by worst severity grade observed. Tables should indicate related and unrelated events.

The clinical landscape of COVID-19 treatment continues to evolve, with a number of clinical trials of camostat ongoing globally. During the trial and prior to the final analysis, a data analysis and/or statistical review, may be performed. This review may include available information from other Camostat trials globally, to provide a recommendation to either continue or stop accrual for efficacy or for futility based on available clinical data. Prior to conducting such a review, criteria for decision making will be defined and agreed with the TSC.

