2 SYNOPSIS

Study Title	A Randomised Phase II trial in early COVID-19, assessing use of camostat by blocking SARS-CoV-2 Spike protein-initiated membrane fusion.
Short title	SPIKE-1
Sponsor	Cancer Research UK
Funder	LifeArc
Trial Design	
A randomised, multicentre, prospective, open label, community-based clinical trial.
 
There are two arms:
 
Treatment arm: Patient to receive treatment with camostat tablets, 200mg four times daily (qds) for 14 days
 
Control arm (non-treatment): Patient to receive best supportive care.
 
Patients will be randomised 1:1 into each of these arms until both arms have recruited up to 50 patients.
 
Early assessment of recruitment and trial feasibility will be critical therefore the Trial Management Group (TMG) will provide ongoing review of these aspects and propose modification for regulatory/ethical approval as appropriate.

Trial patients	
 ▪ Adults, 18 years of age and above ▪ Symptomatic COVID-19 infection ▪ Evidence of current COVID-19 infection from a validated assay 
Patients will be recruited through various methods including but not limited to:
 
 • General Practitioner (GP) practices • Advertisement (e.g. on social media, at testing centres) • COVID hubs • Identification through other hospital departments (e.g. Emergency Departments, Acute Assessment Units, Oncology etc.) • NHS Digital • Hospital in-patients • Test and Trace, or equivalent
Sample size	Up to 100 patients (randomised 1:1 treatment and control arm).
Planned trial period	Start date August 2020. The anticipated end date for this trial is July 2021, however that may be amended based on emerging data and circumstances.
Planned recruitment period	Approximately 12 months
Primary Objective and Endpoint	
Objective	Endpoint
To further assess the safety and toxicity profile of camostat. to support integration into a Phase III trial.	Causality and severity of each adverse event (AE) to camostat.
Secondary Objectives and Endpoints	

To confirm that the PK profile aligns with the established PK profile for the active metabolite of camostat, 4-(4-guanidinobenzoyloxy) phenyl acetic acid (GBPA).	Confirm PK parameters of GBPA as assessed by population estimates from population PK analysis (popPK).

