4. TRIAL DESIGN

Table 1: Trial Design

A	Study design	This is a randomised, multi centre, Phase II, prospective open label clinical trial.
---	--------------	--

		
There are two arms:
 
Treatment arm: Patient to receive treatment with camostat tablets, 200mg four times daily (qds) for 14 days
 
Control arm (non-treatment): Patient to receive best supportive care.

B	Patient group	Patients with COVID-19 infection who are symptomatic
C	Sample size	Up to 100 patients will be entered into this trial. Up to 50 patients in each arm. Patients will be randomised 1:1 into each arm.
D	Study intervention	
Patients in the treatment arm will be asked to take camostat for 14 consecutive days and patients in the control arm will be asked to continue with best supportive care.
 
Both groups will be asked to take [REDACTED] A clinical research team member will call the patient daily during this period. On Days 7 and 14, patients will be visited at home by the clinical research team, for blood draws [REDACTED] [REDACTED] Patients will also be called weekly (Days 21 and 28) before the follow up period ends.
 
Patients who are in hospital for non COVID-19 related reasons, who test positive for COVID-19, may also be recruited. Phone calls / home visits will be conducted where possible within hospital face to face.

E	Study analysis	Statistical Analysis Plan (Version 1.0, dated 27Sep2021)

For full details of the trial design, background and rationale for the study, please refer to the current study protocol.

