6.6 Safety

Descriptive statistics will be used for evaluation of safety. The incidence of AEs will be summarised and displayed in frequency tables using counts and percentages. Additional parameters including but not limited to [REDACTED], and laboratory results will also be considered when evaluating safety.

Deaths, serious adverse events (SAEs) and events resulting in trial discontinuation will be tabulated.

Additional safety analyses may be determined at any time, in order to most clearly enumerate rates of toxicities and to further define the safety profile of camostat.

- The safety population is composed by all patients that receive at least one dose of camostat / complete Day 1 of control arm. The safety patient population will be used for the general safety presentations.

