6.7 Adverse Events

For patients on the treatment arm Pre-treatment AE's will be defined as those where "Did this AE start prior to first dose of IMP?" is ticked. Treatment Emergent AE's will be defined as those where "Did this AE start prior to first dose of IMP?" is not ticked. For patients on the control arm pre-treatment AE's will be defined as those where the AE started prior to Day 1. Treatment emergent AE's will be defined as those where the AE started after and inclusive of Day 1.

Treatment related AE's are those where causality to IMP is considered to be Possible, Probable or Highly Probable.

COVID-19 related AE's will be defined as those where "Is this AE related to COVID-19" is ticked yes.

The frequency of AEs will be summarised overall and by treatment arm. A patient can be counted multiple times per row for the No. of Episodes but will only be counted once per row for the No. of Patients.

Table 5: Frequency of All Adverse Events

Safety population

MedDRA System Organ Class (SOC) MedDRA Preferred Term	No. of Episodes Reported	No. of Patients N=XX	No. of Patients in Treatment Arm N=XX	No. of Patients in Control Arm N=XX
All AE's	N	N (%)	N (%)	N (%)
BLOOD AND LYMPHATIC...				
Anemia				
CARDIAC DISORDERS				
Sinus tachycardia				
Etc				

There will be additional versions of the above table based on pre-treatment AE's, treatment emergent AE's, treatment emergent SAE's (any AE that is considered Serious), related treatment emergent AE's. COVID-19 related AE's.

Overview of treatment emergent adverse events (by treatment arm). An AE is considered to have led to withdrawal if an adverse event with "Did the AE cause the subject to be discontinued from the study?" is recorded as yes.

Table 6: Overview of Treatment Emergent Adverse Events (Inclusive and post Day 1)

Safety population

Patients with TEAEs	Overall No. of Patients N=XX	No. of Patients in Treatment arm N=XX	No. of Patients in Control arm N=XX
Patients with >=1 TEAE	N (%)	N (%)	N (%)
Patients with >= 1 TE SAE			
Patients with >= 1 COVID-19 related			
Patients with >= 1 Treatment related			
Patients with >= 1 AE leading to withdrawal			
Patients who died			

Treatment emergent adverse events leading to withdrawal of treatment will be listed by patient. Patients will be included if an adverse event has "Action taken" recorded as "Drug Withdrawn" or "Did the AE cause the subject to be discontinued from the study?" is recorded as yes.

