12 LIST OF ANALYSES

Although the sample size has been calculated on recruitment rate, the primary outcome will be the comparison of adverse events and their severity between treatment arms. These will be listed overall and by strata.

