12.2 Main study findings

The primary outcomes for this trial are safety and adverse events. These will be tabulated by treatment group and by strata/subgroups. Pregnancy, compliance, protocol deviations will also be tabulated in this way.

The majority of secondary outcomes will be reported in the main RAP. The secondary outcomes of number of oxygen-free days, ventilator-free days, and number of days to worst point on the 9-point ordinal scale (see secondary objectives in RAP for definitions) will be reported as median and range for the 28 days of follow up post-randomisation.

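### A plain standard error for binary differences is zero or too small when an arm has no events; a score-type 95% interval should replace it

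*Protocol*

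**What the plan says.** **Secondary outcomes.** The rule for binary data, in protocol 13.1 and again in SAP section 10, is: "Absolute percentage difference and standard error will be reported for binary variables". It sits in the paragraph on secondary outcomes. Of the secondary endpoints in protocol section 4, only COVID-19 related hospital admission is clearly binary. SAP 12.2 and 12.4 summarise oxygen-free days, ventilator-free days and time to worst point by median and range. RAP Table 11, where admission is summarised, has count and proportion rows for all patients and for each arm. It has no column for a difference or its precision.

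**Primary outcome.** SAP section 12 states that "the primary outcome will be the comparison of adverse events and their severity between treatment arms". The methods given for it are descriptive. RAP 6.6 says "The incidence of AEs will be summarised and displayed in frequency tables using counts and percentages", RAP 6.7 says "The frequency of AEs will be summarised overall and by treatment arm", and SAP 12.2 adds "These will be tabulated by treatment group and by strata/subgroups". Tables 5 and 6 give numbers and percentages per arm, with no between-arm estimate.

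**Size and purpose.** RAP section 4 allows "Up to 50 patients in each arm". Protocol 13.1 also says "No significance testing will be performed" and that between-arm differences are there only to inform later trials.

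**The concern.** The unpooled standard error is built from the observed proportions. An arm with no events contributes nothing to it, although 0 out of 50 is far from proof of zero risk. If both arms are empty, the report would show a difference of 0 with a standard error of 0, which reads as perfect knowledge. Someone planning a later trial from that line would be misled about how large a difference remains possible.

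The primary outcome has a milder form of the same gap. It is described as a comparison between arms, but the reader gets two percentages and no indication of how far apart the underlying rates could be.

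**Working it through.** **Inputs.** 50 per arm is the maximum in both documents. Efficacy denominators can only be smaller, because that population requires five days of camostat, or completion to Day 14 or an endpoint. Event counts and true risks below are assumptions, since the documents give no expected admission rate. The unpooled standard error is also an assumption, since no formula is named.

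**The plan's own precision figure.** The documents state none for admission or adverse events. The one they state, for recruitment in protocol 13.2, reproduces with 100 recruited out of 200 approached: SE = sqrt(0.5 x 0.5 / 200) = 3.5%, and 50% plus or minus 1.96 x 3.54% = 43% to 57%.

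**Formulas.**
- Standard error of the difference: SE = sqrt[p1(1-p1)/50 + p2(1-p2)/50].
- Newcombe: with Wilson limits (l, u) for each arm and d = p1 - p2, lower = d - sqrt[(p1-l1)^2 + (u2-p2)^2] and upper = d + sqrt[(u1-p1)^2 + (p2-l2)^2].

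**0 v 0.** SE = 0. The Wilson upper limit for 0/50 is 1.96^2/(50 + 1.96^2) = 7.1%, so Newcombe is -7.1 to +7.1 points.

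**0 v 4.** d = -8 points. SE = sqrt(0 + 0.08 x 0.92/50) = 3.84 points, so d plus or minus 1.96 SE is -15.5 to -0.5. The Wilson limits are 0 to 7.13% for 0/50 and 3.15% to 18.84% for 4/50. The Newcombe lower limit is -8 - 10.84 = -18.8. The upper limit is -8 + sqrt(7.13^2 + 4.85^2) = -8 + 8.62 = +0.6.

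| Events (of 50 v 50) | SE, points | d +/- 1.96 SE | Newcombe 95% |
|---|---|---|---|
| 0 v 0 | 0 | 0 to 0 | -7.1 to +7.1 |
| 0 v 1 | 1.98 | -5.9 to +1.9 | -10.5 to +5.3 |
| 0 v 4 | 3.84 | -15.5 to -0.5 | -18.8 to +0.6 |

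**Miettinen-Nurminen.** This inverts the score statistic, using restricted maximum-likelihood variances multiplied by 100/99. It gives -7.2 to +7.2 for 0 v 0 and -18.9 to -0.5 for 0 v 4. The two methods agree on the far limit, which the plain standard error understates by about 3 points, but differ on whether 0 v 4 reaches zero.

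**How often this arises.** One arm is empty with probability (1-p)^50. At 1% that is 0.605, so at least one arm is empty with probability 1 - (1-0.605)^2 = 84% and both with 0.605^2 = 37%. At 2% it is 0.364, giving 60% and 13%. At 5% v 10% it is 0.077 and 0.005, giving 0.077 + 0.005 - 0.0004 = 8% for at least one.

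**Coverage, by summing over all outcomes of two binomials of size 50.**

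| True risks | d +/- 1.96 SE | Newcombe |
|---|---|---|
| 1% v 1% | 99.8% | 100% |
| 2% v 2% | 98.7% | 99.8% |
| 2% v 4% | 86% | 99.2% |
| 5% v 10% | 94.7% | 96.9% |

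**Single-arm safety precision.** The exact two-sided 95% upper limit for 0/50 is 1 - 0.025^(1/50) = 7.1%.

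**The case against.** The strongest reply is that this is a descriptive trial. It promises a standard error, not a Wald interval, and plans no tests. With counts and proportions shown by arm, anyone who sees 0/50 v 0/50 can work out an interval. The rule reaches essentially one outcome, and nothing in the documents says admission will be rare: recruitment also runs through emergency departments and hospital wards. At 5% v 10% the plain standard error performs acceptably. All of this stands, and it limits the point to sparse data. It does not defend the standard error itself, since the plan chose to report a precision measure and that measure fails in exactly the sparse case.

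Three stronger readings are tempting and are not supported.
- A reader might infer that the method under-covers generally. It does so at low, unequal risks. At equal risks of 1% or 2% coverage is about 99% to 100%, because an interval of 0 to 0 contains a true difference of zero.
- A reader might infer that it will produce false claims of a difference. The plan draws no such conclusions, and for 0 v 4 the Miettinen-Nurminen interval also stops short of zero.
- A reader might infer that the safety analysis is deficient. Protocol 13.1 frames the primary outcome as exploratory and descriptive, and frequency tables are a legitimate way to present it. The case for adding differences rests on SAP section 12 calling it a comparison. Nor does sizing the trial on recruitment add to the point: both documents say openly that this was the basis.

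**Conclusion.** The point holds as a gap in reporting precision. It is not a bias or an error-rate fault. At 50 per arm, the stated summary shows a standard error of 0 where differences of about 7 points either way remain compatible with the data. For 0 v 4 it places the far limit about 3 points too close. The conclusion rests on two assumptions: that the unspecified standard error is the usual unpooled one, and that admissions are few enough for an empty arm to be likely. If risks are nearer 5% and 10%, the practical consequence is small.

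For adverse events, adding a between-arm estimate is a worthwhile extension. Protocol 3.3.1 puts known reactions in the licensed indications below 1%. At exactly 1%, an arm of 50 would show no case with probability 0.99^50 = 60%.

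**What to change.** 1. In protocol 13.1 and SAP section 10, replace the standard error for binary variables with a 95% Newcombe confidence interval for the difference (Miettinen-Nurminen is an acceptable alternative). Name one method in advance, since the two can differ at the margin.
2. Add the difference and interval to the hospital-admission row of RAP Table 11.
3. As an inexpensive addition, give the same risk difference and interval in the Table 6 rows that can occur in both arms: any treatment-emergent event, any serious one, COVID-19 related, leading to withdrawal, and death. Leave out the treatment-related row. RAP 6.7 defines it by causality to the study drug, which controls do not receive, so a between-arm interval has no meaning there. Give that row an exact binomial interval in the camostat arm only, with a note that 0/50 excludes only rates above 7.1%.

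The cost is a few lines of SAS, one changed sentence in each document and slightly wider intervals. No extra data are needed and no hypothesis test is introduced.

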5.1 Patient Populations

The analysis sets are defined as follows:

Full Analysis Population (FAP):	All enrolled patients.
	Patients who are enrolled in error onto the trial (due to ineligibility/administrative error), prior to receiving study treatment, will be excluded from the FAP.
Safety Population:	All enrolled patients who received at least one dose of camostat (or complete Day 1 of the control arm). Safety data will be collected from the date of written consent.
Efficacy Population:	Treatment arm patients must receive camostat for a minimum of five days, and control arm patients must either complete up to Day 14 or come off trial at an earlier timepoint due to an endpoint (e.g. hospitalisation).
Pharmacokinetic Population:	All enrolled patients who received one dose of camostat (or complete Day 1 of the control arm) – PK sample required (optional).

All other populations will be the same definition as Efficacy Population as defined above.

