	
Time frame: Days 7 and 14
 
Information to be presented: Median and range for each arm at each time point for each arm (to be provided in final PK report).

	
Measure Title: PK parameter to confirm half-life (T1/2) of GBPA

	
Measure Description: Half-life (T1/2) of GBPA as assessed by population estimates from population PK analysis

		
Time frame: Days 7 and 14
 
Information to be presented: Mean and standard deviation for each arm at each time point for each arm (to be provided in final PK report).

To assess the ability of camostat to reduce the requirement for COVID-19 related hospital admission in community patients with SARS-CoV-2 infection.	
Rate of COVID-19 related hospital admission in community patients with SARS-CoV-2 infection.
	
Measure Title: Number of community patients admitted to hospital due to COVID-19
 
Measure Description: Number of community patients admitted to hospital due to COVID-19
 
Time frame: Days 1-28
 
Population description: Patients who received camostat for a minimum of five days (treatment arm) or who either completed up to Day 14 or came off trial at an earlier timepoint due to an endpoint defined reason (e.g. hospitalisation).
 
Information to be presented: Number of community patients admitted to hospital due to COVID-19 in each arm from programmed table.

To evaluate the requirement for supplementary oxygen (non-invasive or mechanical invasive) in patients who have received camostat as treatment for SARS-CoV-2 infection.	
Supplementary oxygen-free days at 28 days (from randomisation).
	
Measure Title: Number of oxygen free days
 
Measure Description: Number of oxygen free days
 
Time frame: Days 1-28
 
Population description: Patients who received camostat for a minimum of five days (treatment arm) or who either completed up to Day 14 or came off trial at an earlier timepoint due to an endpoint defined reason (e.g. hospitalisation).

		Information to be presented: Median and range of oxygen free days by treatment arm (provided in Stats report).

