11.1 Populations

The efficacy population will only include patients from the camostat arm where they have completed 5 days of treatment and in the control arm where they have completed 14 days of treatment or reached an endpoint (eg hospitalisation). All primary and secondary analyses will be conducted with this population. An intention-to-treat analysis of the main secondary outcomes (COVID-19 related hospital admissions, supplementary oxygen-free days, ventilator-free days, time to worst point on the 9-point ordinal scale) will also be conducted, should the data allow.

Patients who agree to the taking of blood samples will be included in the analysis of the PK data. The mean and SD will be reported at each time point (Days 7 and 14), as will the mean changes. The data may be log (or other) transformed if not normally distributed. [REDACTED]

[REDACTED] Change will be
change from previous blood test.

The safety population will include all patients with at least one dose of treatment (camostat or control). Safety data will be collected from the date of written consent. Safety variables will be summarised by descriptive statistics.

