12.3 Transformations

12.4 Outputs

Tabular outputs have been described in the main RAP. The following analyses will be in addition to these tables.

Population: Efficacy population (at least 5 days of camostat/14 days of control)

Medians and range for the following variables will be produced by treatment group:

- Number of oxygen-free days,
- Number of ventilator-free days,
- Number of days to worst point on the 9-point ordinal scale

Kaplan-Meier plots of the following variables will be produced by treatment group:

- Time to worst point on ordinal scale

Plots of daily data will also be produced where this will aid interpretation.

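### The efficacy population gives controls an endpoint exception but camostat patients none, so the main efficacy comparison is not one of the randomised groups

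*Protocol*

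**What the plan says.** Protocol 13.1 sets the rule for the efficacy set: "treatment arm patients must receive camostat for a minimum of five days, and control arm patients must either complete up to Day 14". Controls alone have a further way to qualify, which is to "come off trial at an earlier timepoint due to an endpoint", with hospitalisation as the example. SAP sections 5, 5.1 and 10 repeat the rule. SAP 11.1 restates it: "The efficacy population will only include patients from the camostat arm where they have completed 5 days of treatment", while controls need 14 days or an endpoint.

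On the role of this set, SAP 11.1 says "All primary and secondary analyses will be conducted with this population". Tables 10 and 11 in SAP 6.9 (ordinal scale, COVID-19 admission, oxygen-free and ventilator-free days) are headed with it. An intention-to-treat analysis of the four main secondary outcomes "will also be conducted, should the data allow". Neither the table list in SAP 8.2 nor the outputs in SAP 12.4 include an intention-to-treat efficacy table.

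SAP 5.1 also defines a Full Analysis Population of all enrolled patients, less those covered by a clause that begins "Patients who are enrolled in error onto the trial".

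Two places word the efficacy set more loosely. SAP 7.4 adds, after the five-day clause for the treatment arm, "or who either completed up to Day 14 or came off trial at an earlier timepoint due to an endpoint defined reason", with no arm label. The line in SAP 12.4 reads "Population: Efficacy population (at least 5 days of camostat/14 days of control" and does not mention endpoints.

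**The concern.** Membership of the efficacy set is decided after randomisation, by drug exposure in one arm and by follow-up or outcome in the other. In the camostat arm, the events being counted can themselves prevent a patient from qualifying. In the control arm, the same events secure a place. Randomisation does not protect a comparison built that way: an inert drug can show a difference, and the reported standard error carries no allowance for it.

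No test is planned for these outcomes in the protocol, so a false positive is not the issue. Protocol 13.1 says that the differences are reported to inform future trials, and a selection effect would be passed on with them.

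**Working it through.** **Step 1. Follow each kind of patient through the rule in protocol 13.1 and SAP 11.1.** Death is the top category of the ordinal scale, so I read it as an endpoint.

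| Patient | Camostat | Control |
|---|---|---|
| Dies before five days | dropped | kept |
| Admitted early, drug stopped before five days | dropped | kept (admitted early) |
| Admitted early, drug continued to five days | kept | kept (admitted early) |
| Event-free, stops drug before five days | dropped | no counterpart |
| Event-free, leaves between Day 5 and Day 14 | kept | dropped |

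Rows 1, 2 and 5 favour camostat. Row 4 works against it. Row 3 is neutral.

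**Step 2. Inputs.** From the documents: up to 50 patients per arm (protocol synopsis), and an admission outcome restricted to community patients (protocol 4). The documents give no admission, timing or stopping rates, so these are assumptions:
- p = admission risk, 10% in both arms (inert drug)
- f = share of admissions before five days of dosing, 40%
- s = share of those early-admitted camostat patients who stop drug: 0, 0.5 or 1
- g = share of event-free camostat patients stopping before five days, 0 at first
- d = share of event-free controls missing Day 14, 0

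The plan has no figure of its own for this point. Its one precision figure, the recruitment rate in protocol 13.2, does not depend on the efficacy set.

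**Step 3. Formulas.**
- Camostat = p(1 − fs) / [p(1 − fs) + (1 − p)(1 − g)]
- Control = p / [p + (1 − p)(1 − d)]

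**Step 4. Results.** Expected admissions are 50 × 0.10 = 5 per arm, of which 5 × 0.4 = 2 are early.

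| s | Camostat | Control | Difference | Ratio |
|---|---|---|---|---|
| 0 | 0.10/1.00 = 10% (5/50) | 10% | 0 | 1.00 |
| 0.5 | 0.08/0.98 = 8.2% (4/49) | 10% | −1.8 points | 0.82 |
| 1 | 0.06/0.96 = 6.25% (3/48) | 10% | −3.75 points | 0.625 |

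The standard error of a difference is √(2 × 0.1 × 0.9/50) = 6.0 points. Fifty community patients per arm is an upper limit, because in-patients may be recruited; at 30 per arm it is 7.7 points.

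**Step 5. Range.** With no other exclusions, p from 5% to 20% and f from 25% to 50%, the ratio is 1.00 if nobody stops. It runs from 0.90 (p = 20%, f = 25%, half stop) to 0.51 (p = 5%, f = 50%, all stop).

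**Step 6. The opposite pull.** With d = 0 the two effects cancel when g = fs. At s = 0.5 that is g = 0.20: 0.08/(0.08 + 0.9 × 0.8) = 10%. If nobody stops at admission but g = 0.20, camostat is 0.10/(0.10 + 0.72) = 12.2% against 10%, so an inert drug looks worse.

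**Step 7. Day counts.** At 10% admission, 45 of 50 patients are never admitted. If oxygen use is confined to admitted patients, the median of oxygen-free and ventilator-free days is the maximum whether or not up to two patients are removed. Only the range could move. I did not quantify time to worst point.

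**The case against.** The best defence is that the plan already limits the damage. The primary outcome is safety and the efficacy comparisons are descriptive. Intention-to-treat is named in advance for exactly the four outcomes that matter. Early deaths stay visible by arm in the safety tables and the mortality table (SAP 6.7 and 7.3), and exclusions from the efficacy analysis are listed (SAP 8.1). Protocol 5.3.5 and 8.5 intend camostat to continue after admission unless the patient's condition or other care rules it out, and protocol 5.3.3 allows a restart after a short interruption. Admission alone therefore does not exclude anyone, and the illustrated shift is below one standard error.

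Most of this stands, and it limits the weight of the point. It does not remove it. Intention-to-treat is subordinate and conditional, the safety tables do not correct the efficacy estimates, and death before five days of drug always excludes a camostat patient.

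A reader might go further in three ways that the documents do not support:
- *That the rule favours camostat.* Step 6 shows that it can work either way, and no rates are given to settle it.
- *That SAP 7.4 and 12.4 define two further sets, so that wording alone decides whether an inert drug looks better or worse.* The unlabelled clause in 7.4 follows one labelled for the treatment arm, so it most naturally means controls. The bracket in 12.4 reads as shorthand for the set already defined in 5.1 and 11.1, and the outputs listed there do not include admission. A contrast from 12.4 would also need an assumed share of control admissions lost, which the documents do not give. These are consistency edits, with no effect size attached.
- *That the primary safety comparison is restricted in the same way.* The sentence in SAP 11.1 covers primary analyses if taken literally, but SAP 6.6 and 6.7 place the adverse event tables on the Safety Population. This point is confined to efficacy.

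**Conclusion.** The point holds. The main efficacy analysis selects patients after randomisation by different rules in the two arms, and the all-randomised comparison is left as an optional extra. This follows from the text and needs no assumed rate.

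The size does rest on assumptions. On those in step 2, the spurious difference in admission is 0 to 3.75 points in favour of camostat. It is zero if every early-admitted patient reaches five days of drug, and it shrinks or reverses if event-free camostat patients also stop early. Medians of the day counts would probably change little. This should be fixed because the estimates are meant for future trials, but it does not threaten the trial's primary purpose.

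**What to change.** 1. Make the comparison of all randomised patients by assigned arm the main analysis for COVID-19 admission (community patients), oxygen-free days, ventilator-free days and the ordinal outcome. Delete the condition in SAP 11.1. Build the analysis on the Full Analysis Population. Judge its enrolment-error exclusion without regard to arm or outcome, with the same cut-off in both arms; the present cut-off, before study treatment, has no meaning for controls.
2. State in advance how deaths enter the day counts (for example, zero free days for death by Day 28) and how incomplete Day 28 follow-up is handled. Use the multiple imputation in SAP 11.2 as the sensitivity analysis.
3. Keep the five-day exposure set only as a supportive analysis, labelled as non-randomised, with the endpoint exception applied equally to both arms. Tabulate exclusions by arm with the number admitted or dead.
4. Use one definition in protocol 13.1 and SAP 5, 5.1, 7.4, 10, 11.1 and 12.4.

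The cost is SAP wording, re-pointed efficacy tables and a wording amendment to protocol 13.1, which may need review under protocol 15.4. No new visits are needed: patients who only stop drug stay in follow-up (protocol 11), and hospital and primary care records are already reviewed for Days 1 to 28 (protocol 8.3.4). The downside is some dilution from patients who took little drug.
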